6.4 Adjustment for covariate

Adjustment for covariate is not planned.

6.5 Multiple Comparison or Multiplicity of Testing

Multiple comparison or analysis of multiplicity of testing is not planned.

6.6 Interim Analysis

Interim analysis is not planned.

6.7 Sensitivity Analysis

Sensitivity analysis is not planned.

6.8 Study Participation

6.8.1 Subject Disposition

Subjects who completed the study and subjects who discontinued the study are presented using frequency and percentage. For those who discontinued the study, reason for discontinuation is presented using frequency and percentage.

6.8.2 Subject Disposition by Study Site

Subjects who completed the study and subjects who discontinued the study are presented by study site using frequency and percentage.

6.8.3 Protocol Deviation

For subjects with protocol deviation, excluding those who discontinued the study, reason for deviation is presented using frequency and percentage.

6.8.4 Analysis Sets

Number of subjects included in the Safety Analysis Set, FAS, and PPS is presented. Reason for exclusion from the data set is presented using frequency and percentage.

6.9 Demographic Information

Demographic and baseline disease characteristics, past/current disease, previous/concomitant medication, previous/concomitant medication (anti-epileptic drug), and concomitant non-pharmacological therapy at the time of enrollment are analyzed in the FAS.

- **Demographic characteristics**

Continuous data (age, height, body weight, BMI) is presented using descriptive statistics (number of subjects, mean, standard deviation, median (minimum, maximum)), and categorical data (age group (<65 years or ≥65 years), sex) is presented using frequency and percentage.

- $BMI (kg/m^2) = \text{body weight (kg)} / \text{height (m)}^2$

- **Baseline disease characteristics (epilepsy diagnosis: duration of disease, ILAE classification, cause, seizure type and frequency: partial-onset seizure with or without secondary generalization, simple partial seizure with motor involvement, complex partial seizure, complex partial seizure with secondary generalization, other seizures)**

Continuous data (duration of disease, partial-onset seizure with or without secondary generalization, simple partial seizure with motor involvement, complex partial seizure, complex partial seizure with secondary generalization, other seizures) is presented using descriptive statistics (number of subjects, mean, standard deviation, median (minimum, maximum)); for seizure type and frequency, 1st and 3rd quartiles are presented as well. Categorical data (ILAE classification, cause) is presented using frequency and percentage.

- Duration of disease (years) = (date of signing the consent form – date of initial diagnosis) / 365.25
- Seizure frequency = (number of seizures / (date of Visit 1 – date of 8 weeks prior to Visit 1)) x 28

▪ **Past and Current Medical History**

Diseases/procedures in past/current medical history are coded using SOC (System Organ Class) and PT (Preferred Term) of MedDRA (21.0 version). Represented codes are presented using frequency, percentage, and count.

Past medical history is defined as medical history 'not ongoing' at the time of visit, while current medical history is defined as medical history 'ongoing' at the time of visit.

▪ **Previous and Concomitant Medication**

Previous and concomitant medications are coded using 1st level (Anatomical main group) and 4th level (Chemical subgroup) of ATC classification system (2018 version). Represented codes are presented using frequency, percentage, and count.

Previous medications are defined as those taken before the study treatment, while concomitant medications are defined as those taken after the study treatment. Any medication for which the date of last dose is 'UK' (thus, it is not known whether the drug was administered before or after the study treatment) is included in both previous and concomitant medications.

▪ **Previous and Concomitant Medications (anti-epileptic drugs)**

Previous and concomitant medications (anti-epileptic drugs) are coded using 4st level (Chemical subgroup) and 5nd level (Chemical substance) of ATC classification system (2018 version).

Represented codes are presented using frequency, percentage, and count.

Previous medications are defined as those taken before the study treatment, while concomitant medications are defined as those taken after the study treatment. Any medication for which the date of last dose is 'UK' (thus, it is not known whether the drug was administered before or after the study treatment) is included in both previous and concomitant medications.

▪ **Concomitant Non-Pharmacological Therapy**

Concomitant non-pharmacological therapies are coded using SOC (System Organ Class) and PT (Preferred Term) of MedDRA (21.0 version). Represented codes are presented using frequency, percentage, and count.

6.10 Treatment Compliance

Treatment compliance during the study period is calculated as follows, and presented using descriptive statistics (number of subjects, mean, standard deviation, median, minimum, and maximum).

$$\text{Treatment compliance (\%)} = \frac{\text{Actual number of administration days during the study period}}{\text{Expected number of administration days during the study period}} \times 100$$

6.11 Efficacy Analysis

In the efficacy analyses, seizure frequency is calculated as follows.

- Seizure frequency during the screening period = (number of seizure / (date of Visit 1 – date of 8 weeks prior to Visit 1)) x 28
- Seizure frequency during the titration period = (number of seizure / (date of end of Visit 3 or date of withdrawal during the titration period – date of start of Visit 2)) x 28
- Seizure frequency during the maintenance period = (number of seizure / (date of end of Visit 5 or date of withdrawal during the maintenance period – date of start of Visit 4)) x 28

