9.7.1.5 Efficacy Analyses

The efficacy analysis will be performed on the Full Analysis Set. The analysis performed on Per Protocol Analysis Set will be supportive. This is a single-arm study having no reference arm. Therefore, formal hypothetical inferences are not necessary and only descriptive statistics will be given. Continuous variables will be summarized with mean, standard deviation, median, minimum and maximum. Categorical variables will be summarized by number and percentages of subjects. Seizure frequency will be based on number of seizures per 28 days, calculated as the number of seizures over the entire time interval divided by the number of days in the interval and multiplied by 28. (Amendment 02)

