6.11.2 Analysis of secondary efficacy endpoints.....	16

[figure not shown]

Statistical Analysis Plan

6.12	Safety Analysis.....	18
6.12.1	Extent or Exposure.....	18
6.12.2	Adverse Events.....	18
6.12.3	Laboratory Tests	19
6.12.4	Vital Signs	19
6.12.5	Physical Measurement (Body Weight)	19
7.	Plan for Revision of Analysis Method	19
8.	TLF shell	19
9.	Roles and Responsibilities	22
10.	Applied SOPs	22
11.	Applied SOP SDs	22

1. Study Design

This is a multicenter, open label, single arm, for therapeutic use, study.

Prior to the study initiation, approval from IRB of each study site as well as written contract is required. Prior to the study participation, patients should receive sufficient explanation about the study and provide written consent regarding the access to and use of personal and medical information. After the consent process, subjects who meet all of the inclusion criteria and none of the exclusion criteria will receive the investigational product (Fycompa film-coated tablet). Information on baseline seizure count (frequency) will be collected retrospectively by the subject or guardian. This study consists of titration period (12 weeks) and maintenance period (24 weeks).

[Titration period (12 weeks)]

Subjects will initiate perampanel at 2 mg/day, which can be increased up to 12 mg by increments of 2 mg no more frequently than at 2-week interval according to the investigator's judgment. The dose can be maintained or reduced based on the subject's clinical response and tolerability according to the investigator's judgment. Subjects who cannot tolerate 4 mg/day will be withdrawn from the study. Subjects who are taking concomitant drugs that shorten the half-life of perampanel (phenytoin, carbamazepine, oxcarbazepine, etc.) will titrate the dose by increments of 2 mg/day no more frequently than at 1-week interval. Adjusting the type or dose of concomitant anti-epileptic drug is not allowed during this period.

[Maintenance period (24 weeks)]

Throughout the maintenance period, subjects will maintain the dose administered at the end of the titration period. However, the dose can be increased to maximum 12 mg/day or reduced to minimum 4 mg/day based on the subject's clinical response and tolerability according to the

CONFIDENTIAL

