investigator's judgment. Subjects who reduce the dose during the maintenance period can increase the dose once tolerability is improved. Subjects who cannot tolerate 4 mg/day will be withdrawn from the study. Adjusting the type or dose of concomitant anti-epileptic drug is not allowed during this period.

In case of withdrawal, the dose will be tapered down and follow-up visit will take place 4 weeks after the last dose.

Subjects will visit the site for Visit 1 (Week 0), Visit 2 (Week 6), Visit 3 (Week 12), Visit 4 (Week 24) and Visit 5 (Week 36).

2. Study Objectives

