4.1 Efficacy Endpoints

4.1.1 Primary Efficacy Endpoint

50% responder rate for partial onset seizures with or without secondary generalization: the proportion of subjects achieving at least 50% reduction in the frequency of partial onset seizures with or without secondary generalization during the maintenance period compared to baseline

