5.1 Efficacy Analysis Set

Efficacy is analyzed primarily in the Full Analysis Set (FAS), and secondarily in the Per-Protocol Set (PPS). Safety is analyzed in the Safety Analysis Set.

- FAS: subjects who received at least one dose of investigational product and were assessed for primary efficacy at least once during the maintenance period (Week 12 - 5 days ~ Week 36 + 7 days).
- PPS: subjects in FAS who completed the study per protocol without major violation. Subjects who meet any of the following conditions are excluded from PPS.
 - 1) Deviation from selection criteria
 - 2) Use of prohibited concomitant medication or therapy
 - 3) Withdrawal
 - 4) Deviation from treatment compliance
 - 5) Other deviation considered as major protocol violation

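### SAP 6.11 starts the titration and maintenance seizure-frequency spans at Visits 2 and 4 (Weeks 6 and 24), which read literally halves both periods; the intended start dates are not defined

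*SAP*

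**What the plan says.** SAP 6.11 gives three formulas, each a seizure count divided by a difference of dates and multiplied by 28.

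- Screening: "date of Visit 1 – date of 8 weeks prior to Visit 1".
- Titration: "date of end of Visit 3 or date of withdrawal during the titration period – date of start of Visit 2".
- Maintenance: "date of end of Visit 5 or date of withdrawal during the maintenance period – date of start of Visit 4".

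The count in each numerator carries no dates. SAP 6.11.1 and 6.11.2 announce a formula for each endpoint, but none follows, so 6.11 is the only place where the SAP states the rule.

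The visit schedule in SAP section 1 includes "Visit 3 (Week 12), Visit 4 (Week 24) and Visit 5 (Week 36", with Visits 1 and 2 at Weeks 0 and 6. Protocol 9.5.2.2.2 puts Visits 2 to 5 at Days 42, 84, 168 and 252. On the periods, SAP section 1 states: "This study consists of titration period (12 weeks) and maintenance period (24 weeks". Protocol 9.1.2 and 9.1.3 set them at Weeks 0-12 and 12-36. SAP 5.1 admits a subject to the FAS on one primary efficacy assessment "during the maintenance period (Week 12 - 5 days ~ Week 36 + 7 days".

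Protocol 9.7.1.5 defines seizure frequency as "calculated as the number of seizures over the entire time interval divided by the number of days in the interval and multiplied by 28".

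**The concern.** The primary endpoint is "the proportion of subjects achieving at least 50% reduction in the frequency of partial onset seizures" in maintenance against baseline, so the maintenance frequency decides who is a responder. If Visit 4 is the Week 24 clinic visit, as everywhere else in both documents, the denominator begins halfway through maintenance. That conflicts with the stated 24-week period, with the FAS window that opens just before Week 12, and with the Protocol rule that the whole interval is used.

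The formula provides for withdrawal during maintenance, but a subject who leaves between Visits 3 and 4 has no Visit 4 date. Such a subject can be in the FAS and still have no frequency. SAP 6.3 allows no imputation, and the SAP does not say whether the subject stays in the responder-rate denominator. The same formulas feed all seven secondary efficacy endpoints. Two programmers working from this text could therefore obtain different results from the same diaries.

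**Working it through.** **Inputs from the documents.** Visits 1 to 5 at Days 0, 42, 84, 168 and 252. Windows of ±5 days at Visits 2 and 3 and ±7 days at Visits 4 and 5 (Protocol 9.5.2.2.2). Planned 105 enrolled and 94 for the primary analysis (Protocol 9.7.2). Entry requires at least 2 seizures in 8 weeks (Protocol 9.3.1).

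**The plan's own period lengths.** 12 weeks × 7 = 84 days and 24 weeks × 7 = 168 days. These equal Visit 3 − Visit 1 = 84 − 0 = 84 and Visit 5 − Visit 3 = 252 − 84 = 168.

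**Spans under the literal formula.**

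| Period | Literal span | Within visit windows | Stated period | Within visit windows |
|---|---|---|---|---|
| Titration | 84 − 42 = 42 | 79 − 47 = 32 to 89 − 37 = 52 | 84 | 79 to 89 |
| Maintenance | 252 − 168 = 84 | 245 − 175 = 70 to 259 − 161 = 98 | 168 | 245 − 89 = 156 to 259 − 79 = 180 |

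**Withdrawals in maintenance.** For withdrawal on Day 182 the literal span is 182 − 168 = 14 days, against 182 − 84 = 98 days of maintenance follow-up. For withdrawal on Day 126 there is no Visit 4 date and so no denominator; from Visit 3 it would be 126 − 84 = 42 days.

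**Diary-interval reading.** If the start of Visit 2 means the start of the diary returned at Visit 2 (Visit 1, Day 0), and the start of Visit 4 likewise means Visit 3 (Day 84), the spans are 84 and 168 days and nothing is wrong.

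**Effect of the literal span with a matched Weeks 24-36 count.**

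1. *One subject at the entry floor* (assumed: Poisson counts, exactly 2 seizures in 56 baseline days, true baseline rate 1 per 28 days). Response needs a frequency of 0.5 per 28 days or less: at most 0.5 × 168/28 = 3 seizures over 168 days, or at most 0.5 × 84/28 = 1.5, so 1 seizure, over 84 days.

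| True reduction | Weeks 12-36: mean, P(≤3) | Weeks 24-36: mean, P(≤1) |
|---|---|---|
| 0% | 6, 15.1% | 3, 19.9% |
| 30% | 4.2, 39.5% | 2.1, 38.0% |
| 50% | 3, 64.7% | 1.5, 55.8% |

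The shift goes in either direction. With no effect, the chance of seizure freedom is exp(−6) = 0.2% over 168 days and exp(−3) = 5.0% over 84.

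2. *A population* (simulated, all inputs assumed: gamma rates with mean 1.5, 3 or 6 per 28 days and shape 0.5, 1 or 2; within-subject variance 1 or 2 times the mean; 30% or 50% reduction; entry filter applied). The 50% responder rate changes by −1.4 to +4.7 points. The seizure-free rate is multiplied by 2.2 to 6.6 if no subject is truly seizure-free, but by only 1.03 to 1.4 if 20% are. In one setting (mean 3, shape 1, variance ratio 2, 30% reduction) it goes from 2.2% to 7.0% with none truly seizure-free, and from 21.7% to 25.6% with 20%.

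3. *Loss of Week 12-24 withdrawals* (assumed: 33 responders among 94 subjects with a computable frequency, plus k withdrawals in the FAS who are all non-responders). Planned drop-outs are 105 − 94 = 11; spread evenly over 36 weeks, 11 × 12/36 = 3.7, or about 4, fall in Weeks 12-24.
   - k = 4: 33/98 = 33.7% if kept, 33/94 = 35.1% if dropped.
   - Range: k = 1 gives 33/95 = 34.7%; k = 11 gives 33/105 = 31.4%; each against 35.1%.

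For scale, the approximate 95% half-width at 33/94 is 1.96 × √(0.351 × 0.649/94) = 9.6 points.

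**The case against.** The strongest reply is that the documents lean towards the harmless meaning. A clinic visit is a single date, and the screening line names Visit 1 plainly as one. The on-treatment lines instead give each visit a start and an end, which suits an interval that closes at the visit. Protocol 9.5.2.2.2 lists Visits 2 and 3 under titration and Visits 4 and 5 under maintenance, matching the formulas, and diaries are reviewed at Visits 2 to 5 (Protocol 9.5.1.2). The maintenance formula accepts withdrawal at any time in that period, which works only if the span starts at Week 12. All of this stands, and it means that a wrong denominator is not proven. It does not remove the point, because no section defines the start or end of a visit and the literal text gives the wrong spans.

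A reader might infer two more serious consequences; the documents support neither.

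- *Doubled frequency*, from a full-period count over half the days. Protocol 9.7.1.5 rules this out by tying seizures and days to the same interval.
- *Negative frequency scored as response*, for a withdrawal before Week 24. This requires inserting the scheduled Day 168 for a visit that never took place. The plan provides for no such substitution, and SAP 6.3 analyses data without imputation.

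**Conclusion.** The point holds as an undefined start date in the primary-endpoint formula. Followed literally, the formula covers half of each period, contradicts the stated periods and Protocol 9.7.1.5, and leaves FAS subjects who withdraw between Visits 3 and 4 without a maintenance frequency. Under the diary-interval meaning there is no error.

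Under the literal span with a matched count, the likely change in the 50% responder rate is small: about −1 to +5 points from the shorter span, and 1.4 points in the four-withdrawal example. Both figures rest on the assumed inputs shown. The seizure-free rate is inflated, by an amount that depends almost wholly on the share of subjects assumed to be truly seizure-free. The efficacy analysis is descriptive and no decision rule is affected. This is a should-fix.

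**What to change.** In SAP 6.11:

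- Start the titration span at the Visit 1 (first dose) date and end it at Visit 3 or at withdrawal during titration.
- Start the maintenance span at the Visit 3 date and end it at Visit 5 or at withdrawal during maintenance.
- State that seizures and days are counted over the same interval, as in Protocol 9.7.1.5.
- In the same edit, say how a FAS subject without a computable maintenance frequency counts in the responder rate.
- Check that the program code uses these dates.

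The cost is a few lines of SAP text and a code check, with no new data. If the sponsor already meant these dates, the new start dates change no result.

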9.5.1.2 Efficacy Assessments

Primary efficacy variable and secondary efficacy variables are based on seizure counts (frequency). Seizure frequency data will be collected in subject diaries by subjects or guardian/legally authorized representative during the study including the Titration Period and the Maintenance Period. Baseline seizure frequency data during 8 weeks prior to the Visit 1 (Week 0) is collected by subjects or guardian/legally authorized representative, retrospectively. The investigators or designees will be given standardized training on seizure identification to ensure that subjects will be educated in the same standardized fashion at each visit. Seizure frequency data in subject diaries will be reviewed with the investigator(s) at Visit 2, 3, 4 and 5.

50% Responder rate

The 50% responder rate is defined the proportion of subjects achieving at least 50% reduction in seizure frequency during the Maintenance Period relative to the Baseline.

75% Responder rate

The 75% responder rate is defined the proportion of subjects achieving at least 75% reduction in seizure frequency during the Maintenance Period relative to the Baseline.

100% Responder rate (seizure free rate)

The 100% responder rate, seizure free rate, is defined the proportion of subjects achieving 100% reduction in seizure frequency during the Maintenance Period relative to the Baseline.

The percent change in total seizure frequency in the Titration and Maintenance Period relative to the Baseline

The Percentage change is defined the reduction rate in seizure frequency during the Titration Period and the Maintenance Period relative to the Baseline.

50% responder rate in secondarily generalized tonic clonic seizures

The 50% responder rate in secondarily generalized tonic clonic seizures is defined the proportion of subjects with secondarily generalized tonic clonic seizures achieving at least 50% reduction in seizure frequency during the Maintenance Period relative to the Baseline.

75% responder rate in secondarily generalized tonic clonic seizures

The 75% responder rate in secondarily generalized tonic clonic seizures is defined the proportion of subjects with secondarily generalized tonic clonic seizures achieving at least 75% reduction in seizure frequency during the Maintenance Period relative to the Baseline.

100% responder rate (seizure free rate) in secondarily generalized tonic clonic seizures

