9.5.2.2.2 TREATMENT PERIOD ASSESSMENTS

TITRATION PERIOD ASSESSMENTS

Visit 2 (Week 6, Day 42±5)

The following procedures and evaluations will be performed:

- Vital signs (systolic and diastolic BP in sitting position, pulse), body temperature
- Record all concomitant medication use.
- Record concomitant AED use.
- Record any AEs.
- Collect unused study drug and record compliance.
- Return and review subject diary.

- Dispense study drug.
- Dispense subject diary.
- Schedule Visit 3.

Visit 3 (Week 12, Day 84±5)

The following procedures and evaluations will be performed:

- Vital signs (systolic and diastolic BP in sitting position, pulse), body temperature
- Record all concomitant medication use.
- Record concomitant AED use.
- Record any AEs.
- Collect unused study drug and record compliance.
- Return and review subject diary.
- Dispense study drug.
- Dispense subject diary.
- Schedule Visit 4.

MAINTENANCE PERIOD ASSESSMENTS**Visit 4 (Week 24, Day 168±7)**

The following procedures and evaluations will be performed:

- Vital signs (systolic and diastolic BP in sitting position, pulse), body temperature
- Record all concomitant medication use.
- Record concomitant AED use.
- Record any AEs.
- Collect unused study drug and record compliance.
- Return and review subject diary.
- Dispense study drug.
- Dispense subject diary.
- Schedule Visit 5.

Visit 5 (Week 36, Day 252±7) or Discontinuation

The following procedures and evaluations will be performed:

- Vital signs (systolic and diastolic BP in sitting position, pulse), body temperature, weight.
- Blood and urine samples for clinical laboratory evaluations and pregnancy testing (serum, only females of childbearing potential)
- Record all concomitant medication use.
- Record concomitant AED use.

- Record any AEs.
- Collect unused study drug and record compliance.
- Return and review subject diary.
- Dispense study drug. (Discontinuation Only) (Amendment 02)
- Dispense subject diary. (Discontinuation Only) (Amendment 02)

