6.3 Handling of Withdrawal and Missing Data

All evaluation data will be analyzed as is without imputation for missing data.

In the analysis of duration of disease, missing month of the date of epilepsy diagnosis will be substituted with June and missing day will be substituted with 15. If the year is missing, the date of epilepsy diagnosis will be handled as missing data. If imputation results in negative duration of disease, the duration of disease will be 0.

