6.11.2 Analysis of secondary efficacy endpoints

1) 75% responder rate for partial onset seizure with or without secondary generalization

Seizure frequency during the screening period and seizure frequency during the maintenance period in 75% responders, defined as subjects achieving at least 75% reduction in the frequency of partial onset seizures with or without secondary generalization during the maintenance period compared to baseline, are presented using descriptive statistics (number of subjects, mean, standard deviation, median (minimum, maximum), 1st quartile, and 3rd quartile), rate, and 95% CI. Seizure frequency is calculated as follows.

2) 100% responder (seizure-free) rate for partial onset seizure with or without secondary generalization

Seizure frequency during the screening period and seizure frequency during the maintenance period in 100% responders (seizure-free subjects), defined as subjects achieving 100% reduction in the frequency of partial onset seizures with or without secondary generalization during the maintenance period compared to baseline, are presented using descriptive statistics (number of subjects, mean, standard deviation, median (minimum, maximum), 1st quartile, and 3rd quartile), rate, and 95% CI. Seizure frequency is calculated as follows.

3) Percent change from baseline in the frequency of partial onset seizure with or without secondary generalization during the titration period and maintenance period

Frequency of partial onset seizure with or without secondary generalization during the screening period, titration period, and maintenance period is presented using descriptive statistics (number of subjects, mean, standard deviation, median (minimum, maximum), 1st quartile, and 3rd quartile). Also, percent change in the frequency of partial onset seizure with or without secondary generalization during the titration period and maintenance period compared to the screening

period is calculated and presented using descriptive statistics (number of subjects, mean, standard deviation, median (minimum, maximum), 1st quartile, and 3rd quartile) along with corresponding 95% CI. Seizure frequency is calculated as follows.

4) 50% responder rate for secondary generalized tonic-clonic seizure

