6.12.5 Physical Measurement (Body Weight)

Results at baseline (Visit 1), Week 36 (Visit 5), end-of-study visit, and follow-up as well as the change from baseline to each timepoint post-treatment are presented using descriptive statistics (number of subjects, mean, standard deviation, median, minimum, and maximum).

7. Plan for Revision of Analysis Method

Revision of analysis method is not planned.

8. TLF shell

List of Tables

Table	Table Description
-------	-------------------

Number	
s1	14.1.1 Subject Disposition - All Enrolled Subject
s2	14.1.2 Subject Disposition by Study Site - All Enrolled Subject
s3	14.1.3 Major Protocol Deviations - All Enrolled Subject
s4	14.1.4 Analysis Sets - All Enrolled Subject
b1	14.1.5 Demographic Characteristics - Full Analysis Set
b2	14.1.6 Baseline Disease Characteristics - Full Analysis Set
b3	14.1.7 Past Medical History - Full Analysis Set
b4	14.1.8 Current Medical History - Full Analysis Set
b5	14.1.9 Previous Medications - Full Analysis Set
b6	14.1.10 Concomitant Medications - Full Analysis Set
b7	14.1.11 Previous Medications (anti-epileptic drugs) - Full Analysis Set
b8	14.1.12 Concomitant Medications (anti-epileptic drugs) - Full Analysis Set
b9	14.1.13 Concomitant Non-Pharmacological Therapy - Full Analysis Set
e1_1	14.2.2.1 50% Responder Rate for Partial Onset Seizures with or without Secondary Generalization - Full Analysis Set
e1_2	14.2.2.2 50% Responder Rate for Partial Onset Seizures with or without Secondary Generalization - Per Protocol Set
e2_1	14.2.3.1 75% Responder and 100% Responder (Seizure-Free) Rate for Partial Onset Seizures with or without Secondary Generalization - Full Analysis Set
e2_2	14.2.3.2 75% Responder and 100% Responder (Seizure-Free) Rate for Partial Onset Seizures with or without Secondary Generalization - Per Protocol Set
e3_1	14.2.4.1 Percent Change in the Frequency of Partial Onset Seizures with or without Secondary Generalization during the Titration Period and Maintenance Period compared to Screening Period - Full Analysis Set
e3_2	14.2.4.2 Percent Change in the Frequency of Partial Onset Seizures with or without Secondary Generalization during the Titration Period and Maintenance Period compared to Screening Period - Per Protocol Set
e4_1	14.2.5.1 - 50% Responder, 75% Responder, and 100% Responder (Seizure-Free) Rate for Secondary Generalized Tonic-Clonic Seizure - Full Analysis Set

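### In the FAS, a subject who leaves early in maintenance without a seizure is counted as seizure-free for a 24-week endpoint

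*SAP*

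**What the plan says.** - **Interval.** SAP 6.11 divides the maintenance seizure count by the days up to the end of Visit 5 "or date of withdrawal during the maintenance period", then multiplies by 28. Protocol 9.7.1.5 uses the same days-in-interval scaling and has no rule for withdrawals.
- **Definition.** SAP 6.11.2 describes "100% responders (seizure-free subjects), defined as subjects achieving 100% reduction in the frequency of partial onset seizures" in the maintenance period. Protocol 9.5.1.2 speaks of the "proportion of subjects achieving 100% reduction in seizure frequency during the Maintenance Period relative to the Baseline". Protocol 9.1.3 sets that period at 24 weeks, Weeks 12 to 36. Neither document adds a completion or minimum-exposure condition.
- **Analysis set.** The FAS in SAP 5.1 takes treated subjects who "were assessed for primary efficacy at least once during the maintenance period". The Visit 5 or Discontinuation list in protocol 9.5.2.2.2 includes "Return and review subject diary", so a subject who attends that visit supplies data.
- **Missing data.** SAP 6.3: "All evaluation data will be analyzed as is without imputation for missing data". SAP 6.7 plans no sensitivity analysis.
- **Supportive set.** SAP 5.1 says "Subjects who meet any of the following conditions are excluded from PPS", and withdrawal is one of those conditions. The responder tables are repeated in the PPS, for example table e2_2 in SAP section 8, "75% Responder and 100% Responder (Seizure-Free) Rate for Partial Onset Seizures with or without Secondary Generalization - Per Protocol Set".

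**The concern.** The endpoint is named for a 24-week period, but a withdrawn subject is judged on whatever part of it was observed. Zero seizures over 7 or 14 days gives a frequency of zero, a 100% reduction, and the same classification as a completer with 168 seizure-free days. A subject who leaves because of intolerance can therefore be reported as a seizure-freedom success.

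Seizure freedom is an uncommon outcome. Protocol 7.3.3.3 lists Phase III rates of 1.5% to 4.8% at 4 to 12 mg, so a few misclassified subjects are a noticeable share of the total. The study is single-arm and descriptive, so the reported rate and its interval are the whole result. The same scoring applies to the secondarily generalized tonic-clonic responder rates.

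**Working it through.** **Inputs**
- Planned maintenance length: 168 days, from Week 12 (protocol 9.1.3).
- Minimum baseline: 2 partial onset seizures in 8 weeks, or 56 days (protocol 9.3.1).
- FAS size: 94, the planned evaluable number (protocol 9.7.2, SAP section 3). It reproduces: (1.96 + 1.282)² × 0.353 × 0.647 / 0.16² = 93.77, rounded up to 94.
- Assumed, because the documents do not give them: baselines above 2, the number and timing of withdrawals, and a Poisson seizure process.

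SAP 6.11 names the start of Visit 4 as the start of the interval. The parallel titration formula runs from the start of Visit 2 to the end of Visit 3. This suggests diary intervals, so maintenance is taken to start at Week 12.

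**Step 1: apply the SAP rule.** For withdrawal on Day 98 (14 days after Week 12) with no seizures, the frequency is 0/14 × 28 = 0. That is a 100% reduction, so the subject is a 100%, 75% and 50% responder.

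**Step 2: chance of no seizures with no drug effect.** P(0 in d days) = exp(−b × d/56), where b is the 8-week baseline count.

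| Baseline b | 14 days | 168 days | Points added per day-14 withdrawal, 100 × P/94 | Three withdrawals |
|---|---|---|---|---|
| 2 | exp(−0.5) = 60.7% | exp(−6) = 0.25% | 0.65 | 1.94 |
| 4 | exp(−1) = 36.8% | below 0.01% | 0.39 | 1.17 |
| 8 | exp(−2) = 13.5% | below 0.01% | 0.14 | 0.43 |
| 16 | exp(−4) = 1.8% | below 0.01% | 0.02 | 0.06 |

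The points are measured against counting the withdrawal as not seizure-free.

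**Step 3: compare the scoring rules.** Assume 10 seizure-free completers and 3 day-14 withdrawals among 94.
- FAS as written, baseline 2: (10 + 3 × 0.607)/94 = 12.6%.
- FAS as written, baseline 8: (10 + 3 × 0.135)/94 = 11.1%.
- PPS, taking only these 3 as excluded: 10/91 = 11.0%.
- Withdrawals counted as not seizure-free: 10/94 = 10.6%.

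If only 4 completers are seizure-free (about the highest Phase III rate) and 37% to 100% of withdrawals are seizure-free while observed, the rule as written gives:
- 3 withdrawals: 5 to 7 of 94 (5.3% to 7.4%)
- 5 withdrawals: 6 to 9 of 94 (6.4% to 9.6%)
- 10 withdrawals: 8 to 14 of 94 (8.5% to 14.9%)

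Counting withdrawals as not seizure-free gives 4/94 = 4.3% in every case.

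**Step 4: the 50% rate.** With true reduction r, a subject responds if X ≤ floor(0.5 × b × d/56), where X is Poisson with mean b(1 − r)d/56 and b is taken as the observed baseline.
- b = 2, r = 0: 60.7% on 14 days, against P(X ≤ 3 | mean 6) = 15.1% on 168 days. The short window inflates the rate.
- b = 8, r = 0.6: exp(−0.4) = 67.0% on 7 days, against P(X ≤ 12 | mean 9.6) = 82.8% on 168 days. The short window lowers it.

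**The case against.** **The effect is small and on a secondary, descriptive endpoint.** In the first illustration the gap is 0.4 to 2.0 points, while the exact 95% interval for 10/94 runs from 5.2% to 18.7%. Protocol 7.3.3.4 reports that adverse events in the extension study were most frequent during titration, so few subjects may leave in maintenance. This stands as a limit on size. It does not make the classification correct.

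**Planned outputs already show much of it.** The PPS tables exclude withdrawals, and SAP 6.8 and 6.12.1 summarise discontinuations, exclusions and maintenance treatment duration. This is partly right. However, the PPS removes these subjects from the denominator and does not count them as not seizure-free, and the primary FAS figure is unchanged.

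**The interval may start at Week 24.** Read literally, a Day-98 withdrawal would have a denominator of −70 days, and the short-interval figures for the 50% and 75% rates would not apply. A zero count still gives frequency zero, so the seizure-free problem remains under either reading.

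**Not every early withdrawal is scored.** A subject lost to follow-up who never returns the post-Week-12 diary has no count, and the SAP does not say how that subject is classified. This stands: the exposed group is those who return a seizure-free diary.

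**The remedy has its own bias.** It treats a withdrawal at day 160 like one at day 7. At baseline 2 with an assumed 90% reduction, exp(−0.6) = 55% would be seizure-free over 168 days, yet every withdrawal would be scored as a failure. That is a real conservative cost. It is acceptable for an endpoint that claims 24 weeks of seizure freedom, and it is why the 50% and 75% rates should get a parallel analysis and keep their present rule.

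**Conclusion.** The concern holds. As written, the FAS rule classifies a subject with a few seizure-free days as seizure-free for the Maintenance Period, and this can only raise that rate. Under the Poisson model with no drug effect, the expected inflation per day-14 withdrawal is 0.02 to 0.65 points among 94 for baselines from 16 down to 2; an individual misclassified subject adds 1/94 = 1.1 points. The total depends on how many subjects withdraw early in maintenance, which the documents do not give. For the 50% and 75% rates there is no fixed direction: the error is upward mainly at low baselines. The correction should be made before database lock, although the number affected may be small.

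**What to change.** 1. In the FAS, define a 100% responder as a subject who completes the Maintenance Period through Visit 5 with no seizures. Keep maintenance withdrawals in the denominator as not seizure-free. Apply this to total seizures and to secondarily generalized tonic-clonic seizures.
2. For the 50% and 75% rates, keep the observed-days analysis and add a parallel one that counts maintenance withdrawals as non-responders.
3. Report the number of maintenance withdrawals and their observed days beside the responder tables.
4. State in SAP 6.11 the date on which the maintenance interval starts.

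The cost is a short SAP edit and one extra column per responder table, using data already collected. The completion condition is new relative to protocol 9.5.1.2, so the SAP should record it as a clarification of that endpoint. The seizure-free rate will be slightly less favourable, because subjects who leave for reasons unrelated to seizures also count as not seizure-free.
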